## 13. STATISTICAL CONSIDERATIONS

### 13.1 Study Overview

This is a randomized phase II trial designed to evaluate the impact of lenalidomide given concurrently with the conjugated 13-valent pneumococcal vaccine (PCV13) versus when PCV13 is administered first and then followed by lenalidomide. We will evaluate serotype-specific antibody responses along with PK and PD markers in each of the treatment arms.

In addition, we will evaluate the clinical efficacy of lenalidomide when given with PCV13 in terms of whether or not a complete response (CR) is achieved in the first two years along with progression-free survival (PFS), incidence of infection, and general toxicity and tolerability of this regimen in this patient population.

### 13.2 Primary Endpoint:

The primary endpoint for evaluation and comparison in this study is the proportion of patients who achieve an antibody response. Following the definitions used by the WHO for serotype-based response as well as recent definitions of antibody response in the literature for multi-valent pneumococcal conjugate vaccine, we will define an antibody response in the context of this trial as achieving at least a four-fold increase in post-vaccination serotype-specific IgG titers or serotype-specific IgG concentrations of  $\geq 0.35 \mu\text{g/mL}$  for 6 of 7 serotypes measured by a standard ELISA assay. These will be measured as changes from baseline compared to repeat assessment 1 month after the second (booster) dose of PCV13.

### 13.3 Study Design

In this trial, patients will be randomized in a 1:1 allocation to receive lenalidomide with PCV13 up front concurrently (Arm A) vs. PCV13 up front and then subsequent administration of lenalidomide (Arm B). In this study we will compare the proportion of patients in each arm who achieve a significant antibody response as defined above. While it is not typical to employ a direct comparison of primary endpoints in the phase II setting, we believe that a randomized phase II design will better control for cohort and sampling variability necessary to assess the primary endpoint. In addition, in a secondary manner, we will also evaluate the clinical efficacy of treatment with lenalidomide in these patients vaccinated with PCV13, where clinical efficacy will be primarily determined through the proportion of patients who achieve a CR within two years (see Analysis Plan for more details).

Randomization will be stratified on exposure to pneumococcal vaccination in the previous 5 years. Those patients who have previously received a polysaccharide pneumococcal vaccine will not be excluded. If a patient drops out of the study prior to administration of a 2nd (booster) pneumococcal vaccination, they will not be considered evaluable for the primary endpoint and will be replaced on the study. However, the patient will be included in analyses of efficacy and tolerability as appropriate.

Assuming that vaccine success in each arm is binomially distributed, we will use a two-sided chi-square test to compare the difference in proportions. We will constrain the Type I error rate in the comparison of vaccine response rates to 0.10. Using a two-sided test, we will have at least 90% power to detect a difference of 0.40 between the two rates (0.20 vs. 0.60) with a total of 44 evaluable patients (22 in each arm). Comparing these two vaccine success rates, if  $p_A \neq p_B$  and the resulting p-value  $< 0.10$ , we will consider the arm with the higher antibody response rate to have a significantly higher rate of vaccine success than the other arm. This design also allows for an interim analysis to be conducted after 11 patients have been accrued to each treatment arm (i.e. 50% of total planned accrual). Under a Lan-DeMets alpha spending function to constrain the Type I error rate, we will consider it sufficient evidence that one arm has a significantly higher antibody response rate than the other arm if the observed p-value  $< 0.0056$  (design generated using East version 5.3).

Independent of the comparison of vaccine-related efficacy, we will also formally evaluate

clinical efficacy using the two-year CR rate. Previous experience with lenalidomide suggests that late responses may be observed. Therefore, to effectively capture evidence of regimen efficacy (beyond the primary endpoint analysis) we will assess the CR rate in a pooled analysis across both arms since the main component of the regimen is lenalidomide therapy. If we find that one arm has shown to be superior to another in terms of antibody response rate as described above, then we will also compare the CR rates between these two arms in an exploratory manner. For the purposes of this trial, if a patient has a documented CR on at least two consecutive evaluations during the first two years, they will be deemed a clinical success. Given the extended time required to observe this clinical endpoint in these patients, we will use a one-stage design. With 44 patients, we will have at least 90% power and a Type I error of 0.10 to be able to detect a 25% or greater true CR rate versus the null hypothesis that the true CR rate is at most 10%. If 8 or more patients are deemed a clinical success as defined above, then we will consider this evidence of efficacy and worth pursuing further. Otherwise, if at most 7 of these 44 evaluable subjects have a CR at the end of two years of follow-up, then we will consider this insufficient clinical activity and may look to modify the treatment regimen to build on observed vaccine response.

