## 1. OBJECTIVES

### 1.1 Primary Objectives

1.1.1 To determine the proportion of early-stage, high-risk CLL patients achieving a response ( $\geq 4$ -fold increase from baseline and/or antibody concentrations  $\geq 0.35 \mu\text{g/mL}$  in 6 of 7 type-specific anti-pneumococcal antibody levels) after 2 doses of pneumococcal 13-valent conjugated vaccine (Prevnar 13, PCV13) administered concurrent with versus sequential to low-dose lenalidomide

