1.2.5 To determine the safety and toxicity associated with long-term lenalidomide exposure

1.2.6 To perform correlative pharmacodynamic and pharmacokinetic studies and correlate these with vaccine/tumor immunologic and disease response.

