**Table 2: Lenalidomide Dosing and Administration**

Treatment Arm	Cycle	Dose	Ancillary Medications	Schedule	Cycle Length
A Concurrent	1	2.5 mg/day	Allopurinol 300 mg/day beginning 3 days prior to lenalidomide and continuing through at least the end of Cycle 1	Days 1-28 continuous	28 days
	2+	5 mg/day	Dexamethasone may be given for up to 7 days during Cycles 1 and 2 for symptomatic tumor flare		

B Sequential	1-3	No lenalidomide	Allopurinol 300 mg/day beginning 3 days prior to lenalidomide and continuing through at least the end of Cycle 4  Dexamethasone may be given for up to 7 days during Cycles 4 and 5 for symptomatic tumor flare	Days 1-28 continuous	
	4	2.5 mg/day			
	5+	5 mg/day			

Lenalidomide dosing and administration are summarized in **Table 2**. Lenalidomide treatment will be administered at 2.5 mg/day during the first cycle of treatment (Arm A: Cycle 1; Arm B: Cycle 4) to minimize risks for tumor flare and/or tumor lysis. The dose of lenalidomide will be increased to 5 mg/day beginning as early as the second cycle of therapy (Arm A: Cycle 2; Arm B: Cycle 5) if all of the following criteria are met on Day 1:

- No clinically significant Grade 3 or greater non-hematologic toxicities attributable to lenalidomide during the preceding cycle.
- Any hematologic toxicity is resolved to  $\leq$  Grade 1.
- Maintained platelet count  $>50K$  at all times during the previous cycle.
- Maintained ANC  $>1K$  at all times during the preceding cycle.
- Any other drug-related adverse events have resolved to Grade  $\leq 1$  severity.

During the first cycle of lenalidomide exposure, and any cycle in which the dose is subsequently escalated, patients are seen on Days 1 and 8 for laboratory evaluation (CBC, chemistries), history, and physical examination to evaluate for tumor lysis and/or tumor flare, respectively. Management of tumor flare response is detailed in **5.2.1** below.

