### 5.1.2 Protein-conjugate 13-valent pneumococcal vaccine

PCV13 administration is summarized in **Table 3** below. Patients will receive 2 doses of PCV13 administered 8 weeks apart. In Arm A (Concurrent), vaccine will be administered on Day 1 of cycles 3 and 5. In Arm B (Sequential), patients will be vaccinated on Day 1 of cycles 1 and 3. Each 0.5 mL dose of vaccine will be given intramuscularly in the deltoid muscle of the upper arm. PCV13 should not be administered intravenously, intradermally, or subcutaneously.

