### 5.3 Duration of Therapy

Patients demonstrating clinical benefit, defined as achievement of an objective response (CR, CRi, or PR) or stable disease (SD), may continue therapy for up to 24 cycles (approximately 2 years) of treatment with lenalidomide. Therapy beyond 24 cycles may be considered after discussion with the principal investigator and consultation with the study sponsor.

Investigators are encouraged to keep patients experiencing clinical benefit on study unless significant toxicity puts the subject at risk or routine noncompliance puts the study outcomes at risk. If the subject meets any 1 of the following criteria, withdrawal from treatment is mandatory:

- Disease progression meeting 2008 IWCLL consensus criteria for treatment.
- Intercurrent illness that prevents further lenalidomide administration.
- Any treatment-related Grade 4 non-hematologic toxicity.
- Unacceptable and/or unmanageable Grade  $\geq 3$  toxicity attributable to lenalidomide.
- Any treatment-related hematologic or non-hematologic toxicity delaying treatment more than 14 days.

- Development of autoimmune hemolytic anemia (AIHA) or immune-mediated thrombocytopenia (ITP)
- Subject elects to withdraw from study or becomes pregnant.
- General or specific changes in the patient's condition rendering the patient unacceptable for further treatment in the judgment of the investigator.
- Subject is noncompliant with study procedures and/or scheduled evaluations.
- Investigator considers withdrawal to be in the best interest of the subject.
- Diagnosis of new or secondary malignancies after initiating treatment

Subjects with inadequate study drug compliance (i.e.  $\leq$  80% of planned doses administered) may be replaced.

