#### 5.4 Duration of Follow Up

Each subject should be followed for at least 30 ( $\pm 7$ ) days after his or her last dose of lenalidomide (i.e. the “safety follow-up period”) to monitor for resolution or progression of AEs and to document the occurrence of new events unless the subject receives a new CLL therapy within this time frame.

Subjects who withdraw consent should still be encouraged to complete the safety follow-up assessments, but these assessments cannot be mandated once consent is withdrawn. Patients removed from study for unacceptable adverse events will be followed until resolution or stabilization of the adverse event.

Beyond the safety follow-up period, patients no longer receiving protocol therapy will continue to be evaluated at 3 month intervals for the first year and every 6 months thereafter until they receive a new CLL therapy, withdraw consent, or expire. Patients may remain in follow-up if disease progression occurs. Required historical, laboratory, and physical examination procedures at each follow-up visit are detailed in the **Study Table** ([Section 10](#)).

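### Patients lost before the booster are dropped from the antibody comparison with no all-randomised check, and the toxicity window omits both Arm B vaccine doses

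*Combined protocol and SAP*

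**What the plan says.** **Antibody response.** The primary objective (1.1.1) concerns response "after 2 doses of pneumococcal 13-valent conjugated vaccine". Section 13.3 randomises 1:1 and compares response proportions with a two-sided chi-square test at 0.10 in 44 evaluable patients, 22 per arm. Of patients who drop out before the booster it says "they will not be considered evaluable for the primary endpoint and will be replaced on the study". They stay in the efficacy and tolerability analyses where appropriate, but the same section defines clinical efficacy mainly through the CR rate. Section 13.4 allows for no more than 10% loss before the booster and a maximum of 24 per arm. The inclusive rule in 13.6.2 concerns tumour response categories.

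**Timing.** Lenalidomide starts at different times ("Arm A: Cycle 1; Arm B: Cycle 4"; 5.1.1, Table 2). Section 5.1.2 states: "In Arm A (Concurrent), vaccine will be administered on Day 1 of cycles 3 and 5". Arm B is vaccinated on Day 1 of Cycles 1 and 3.

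**Stopping.** Section 5.3 lists criteria, several of them toxicities, for which "withdrawal from treatment is mandatory". Section 5.4 then says that "patients no longer receiving protocol therapy will continue to be evaluated at 3 month intervals".

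**Toxicity.** Objective 1.2.5 is "To determine the safety and toxicity associated with long-term lenalidomide exposure", and 13.6.1 makes patients evaluable for toxicity from their first lenalidomide dose. Section 13.5 summarises adverse events by arm and across arms. The Arm B calendar in Section 10 records adverse events from Cycle 1.

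**The concern.** The exclusion in 13.3 takes place after randomisation, and before it the two arms differ both in length of time at risk and in exposure to the drug. If Arm A patients lost before the booster would have responded less often than those who remain, the evaluable-only comparison leans towards Arm A. Section 13.5 would show unequal stopping and the reasons for it, but no planned analysis would show what it did to the antibody comparison.

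The toxicity window raises a separate problem. A vaccine reaction counts in Arm A, while the same reaction in Arm B falls outside the window, yet the arms are summarised side by side. An Arm B patient who leaves before the booster has had vaccine but no lenalidomide. Section 13.3 keeps that patient for tolerability where appropriate, but 13.6.1 never makes that patient evaluable.

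**Working it through.** **The plan's own figure.** Inputs from 13.3: rates 0.20 and 0.60, two-sided alpha 0.10, power 90%. With unpooled variance, n = (1.645 + 1.282)² × (0.2×0.8 + 0.6×0.4) / 0.4² = 21.4, so 22 per arm, with 90.7% power by the same formula. The stated size reproduces. Exact enumeration of the Pearson chi-square test gives 87.7%.

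**Scheduled days (28-day cycles).**
- Arm A booster, Cycle 5 Day 1: 4 × 28 = 112 days, all on lenalidomide.
- Arm B booster, Cycle 3 Day 1: 2 × 28 = 56 days, none on lenalidomide.
- Arm B first lenalidomide, Cycle 4 Day 1: 3 × 28 = 84 days, after both vaccine doses.

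**Effect of selective loss.** Assumptions, not in the documents: true response 40% in both arms, loss fraction d, and response rate r among those lost. The evaluable rate in an arm with loss is (0.40 − d×r)/(1 − d). For d = 0.10 and r = 0 this is 0.40/0.90 = 0.444. Exact enumeration with 22 v 22, Pearson chi-square without continuity correction, p < 0.10:

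| Loss pattern | Wrongly favours A | Total two-sided error |
|---|---|---|
| None | 4.9% | 9.8% |
| A only 5%, r = 0 | 6.5% | 10.1% |
| A only 10%, r = 0 | 8.7% | 11.2% |
| A only 10%, r = 0.20 | 6.6% | 10.1% |
| A only 10%, r = 0.40 (unrelated to response) | 4.9% | 9.8% |
| A 10%, B 5%, both r = 0 | 6.6% | 10.1% |
| A 10%, B 10%, both r = 0 | 4.9% | 9.7% |

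At a true rate of 20%, 10% fully selective loss in Arm A moves the first figure from 5.4% to 7.6%.

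**Invented data.** For 12/22 v 6/22, the difference is 0.273, the pooled rate 18/44 = 0.409 and the standard error √(0.409×0.591×2/22) = 0.148, giving z = 1.84 and p = 0.066. Counting losses as non-response:
- one lost in Arm A (12/23 v 6/22): p = 0.088
- two lost in Arm A (12/24 v 6/22): p = 0.115
- two lost in each arm (12/24 v 6/24): p = 0.074

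**Behaviour of the proposed check.** Assumptions: 24 randomised per arm, no replacement, loss in Arm A only.
- Power at 60% v 20% among boosted patients: at 10% loss, 80.8% all-randomised v 88.7% evaluable-only; at 5% loss, 86.3% v 89.4%.
- Equal true rates of 40%, 10% fully selective loss: all-randomised wrongly favours each arm 5.25% of the time; evaluable-only wrongly favours A 8.95% and B 2.65%.
- Equal true rates of 40%, 10% loss unrelated to response: all-randomised wrongly favours A 2.75% and B 8.90%; evaluable-only gives 5.00% and 5.12%.

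**The case against.** The strongest reply is that the 8.7% is not the plan's scenario. Section 13.4 expects loss in both arms, and at 10% in each, equally selective, the figure is 4.9%, as with no loss. The larger figure needs one-sided and fully selective loss; half-selective loss gives 6.6%. This stands as a limit on size: the bias is possible, not shown.

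The route from toxicity to exclusion is also unproven. Section 13.3 speaks of leaving the study, whereas 5.3 concerns stopping treatment and 5.4 keeps such patients in follow-up. This too stands, but it leaves membership of the primary set undefined for an Arm A patient who stops lenalidomide before the booster.

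Section 13.5 plans serotype-level titre summaries by arm, and 9.1.1 schedules samples before the booster, so partial data could be used. That narrows the gap without showing how exclusion affects the responder comparison.

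Counting losses as non-response has a mirror-image bias against Arm A when loss is unrelated to response. That is correct, and it is why the analysis should be a sensitivity check and not replace the primary.

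On toxicity, adverse events are collected from Arm B Cycle 1, 13.5 sets no start date and the summaries are descriptive. The data therefore exist; the fault lies in the evaluability rule, which conflicts with 13.3.

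**Conclusion.** Both parts hold and should be fixed. The evaluable-only primary fits the objective and need not change, but a post-randomisation exclusion with unequal exposure before it calls for one all-randomised check, and none is planned. At the plan's 10% ceiling, the chance of wrongly favouring Arm A lies between 4.9% and 8.7% in the 40%-response scenarios above, and total two-sided error is at most 11.2%. Where it falls depends on how unequal and how selective the loss is, which the documents do not tell us. The absence of the analysis is certain; the bias is conditional.

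The toxicity point needs no assumption about loss. As written, 13.6.1 places two vaccine doses and 84 days of Arm B outside a by-arm safety comparison that includes both Arm A doses.

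**What to change.** **Section 13.3.** Keep the evaluable-only analysis as primary. Add a sensitivity analysis of all randomised patients in their assigned arms, counting a missing 1-month post-booster titre as non-response and keeping replaced patients in the denominator. Report it beside the primary result with pre-booster losses and reasons by arm, without requiring the two to agree.

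As supporting detail, state which analysis set holds patients who stop lenalidomide before the booster, those whose vaccination is stopped under 6.3.3, and those boosted without a 1-month titre. Section 5.3 also allows replacement of "Subjects with inadequate study drug compliance"; state that this does not remove a patient from the primary endpoint.

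**Section 13.6.1.** Start toxicity evaluability at the first study treatment, PCV13 or lenalidomide, and show Arm B's pre-lenalidomide period separately. Keep the summary from first lenalidomide for objective 1.2.5. This also removes the conflict with 13.3.

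**Cost.** Wording and one extra table, from titres and adverse events already collected, with no change in sample size. Section 9 says the study endpoints have been met and research sampling stops, so the added analysis must be dated and labelled as added late. Its lower power and its conservatism against Arm A when loss is unrelated to response should be stated with it.

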### 2.1.2 Vaccination in patients with CLL

CLL patients typically respond poorly to vaccines, particularly pneumococcal polysaccharide and influenza vaccines. This is especially true in patients with advanced disease stage. In 1960, a series of 42 previously untreated CLL patients was challenged with antigens to mumps, diphtheria, influenza, and typhoid. While there was some correlation between the level of gamma-globulin deficiency and response to antigenic stimulation, this response did not reach that of normal controls, even in patients with normal gamma-globulin levels. In observing these patients over the next year, the patients with the best response to vaccines had the fewest number of bacterial infections.[11] A subsequent study evaluated the responses of patients with hematologic malignancies to influenza vaccines. Eight of the thirteen patients with lymphoproliferative disorders failed to have a four-fold increase in antibody titer with vaccination. Stiver and colleagues demonstrated a 4-fold increase in antibody titer in 36% of patients to influenza A and 32% of those to influenza B. Four patients included in this study had received chemotherapy, and none of these patients had a 4-fold rise in antibody titer in response to vaccination.[12] A correlation between immunologic response to vaccine and absolute numbers of CD4+/CD45RA+ naïve T cells has been identified, which may suggest a role of this subset of cells in antibody response.[13] With a booster, response rates increased from 5% to 15% for influenza A and from 15% to 30% for influenza B, but this did not have a significant impact on protection rates.[14] This poor response was confirmed in an open, randomized study, where the response rates in two doses compared to one was 18% vs 22% for H1N1, 26% vs 14% for H3N2, and 25% vs 22% for influenza B. The results in patients with previous versus current chemotherapy were not statistically different, and patients who had received monoclonal antibody therapy were uniformly poor responders. Of seven patients, there was only one who had a response to influenza B, and no patients responded to H1N1 or H3N2.[15]

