Purified polysaccharide antigens result in T cell-independent type-2 antibody formation. In conjugated vaccines, the polysaccharide antigen is conjugated to a toxoid as a carrier protein, resulting in antibody responses to the polysaccharide antigens in a T cell-dependent way. T cell-dependent antigens induce immunological memory, resulting in the possibility of booster vaccinations. Recent studies have indicated that conjugation of polysaccharides may render the antigen more immunogenic in the CLL population, and there is evidence that patients with CLL have a more significant immune response to

*Haemophilus influenzae* b conjugate than to plain polysaccharide antigen. A statistically significant response to *H. influenza* has been described, where 6 of 28 patients developed a protective antibody level, but no patients in this series had a response to the polysaccharide pneumococcal vaccine. This same study demonstrated a much more robust response to immunizations in control populations than in CLL patients. However, age, disease stage, and IgG levels all play a role in the degree of response to immunization, as illustrated in the study by Hartkamp *et al.* This study showed poor responses to immunization with both the polysaccharide pneumococcal vaccine, as well as the protein-conjugated *H. influenza* vaccine overall. However, a significant correlation was demonstrated with less advanced disease stage and absence of hypogammaglobulinemia, as well as higher levels of total IgG, IgG2, and IgG4 subclasses and lower levels of soluble CD23 (sCD23). Sinsalo *et al* have since reported that 39% of patients achieved a significant response to administration of a 7-valent conjugated pneumococcal vaccine. Responding patients had Binet stage A and had not yet received chemotherapy or developed hypogammaglobulinemia. Responses in more advanced stage of disease were only 5%.

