#### **13.4 Sample Size/Accrual Rate**

We expect that at most 10% will potentially drop out prior to administration of the 2nd vaccination, which translates to a total maximum sample size of  $22+2=24$  in each arm for a total of 48 patients. With an anticipated accrual rate of about 3 patients per month, we expect that this trial will be fully accrued in at most 16 months.

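### Randomisation is stratified on prior pneumococcal vaccination, but the primary chi-square ignores the stratum: a modest efficiency and robustness point

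*Combined protocol and SAP*

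**What the plan says.** Section 13.3 states: "Randomization will be stratified on exposure to pneumococcal vaccination in the previous 5 years". The same section then fixes the primary test: "we will use a two-sided chi-square test to compare the difference in proportions", at a type I error of 0.10, with at least 90% power for 0.20 versus 0.60 and 22 evaluable patients per arm. No stratified test, adjusted estimate or stratified sensitivity analysis for the primary endpoint appears in Sections 13.2 to 13.6.

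Two other passages bear on the point.

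- **Evaluability.** Of patients who leave before the booster, Section 13.3 says "they will not be considered evaluable for the primary endpoint and will be replaced on the study". Section 13.4 sizes this loss: "We expect that at most 10% will potentially drop out prior to administration" of the second vaccination.
- **Endpoint.** Section 13.2 defines response as "at least a four-fold increase in post-vaccination serotype-specific IgG titers or serotype-specific IgG concentrations of" 0.35 µg/mL or more, for 6 of 7 serotypes.

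**The concern.** The plan treats prior vaccination as important enough to be its only stratification factor, and then leaves it out of the analysis. If the factor predicts response, two things follow.

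- **Efficiency.** The unstratified test becomes conservative and gives up some power.
- **Robustness.** Balance at randomisation need not survive into the analysis set, because non-evaluable patients drop out of it and the plan does not say that they are replaced within stratum. The chi-square does not correct for any difference in stratum mix that results.

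There is a reason to expect some association. The concentration limb of the endpoint can be met without a rise, so a higher starting level helps. The documents do not say how strong the association is.

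**Working it through.** **Inputs from the documents (Sections 13.3 and 13.4).** 22 evaluable per arm; response rates 0.20 and 0.60; two-sided 0.10; 24 randomised per arm, with 2 lost.

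**Assumed inputs.** The stratum-response odds ratio (OR), the same in both arms, and the stratum share. Neither is in the documents, so a range is shown.

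**Step 1: the plan's own figure.** The unpooled normal approximation gives 0.40/√[(0.2×0.8 + 0.6×0.4)/22] = 0.40/0.1348 = 2.966. Subtracting 1.645 leaves 1.321, so power is 90.7%, which reproduces the stated 90%. Exact enumeration of the uncorrected Pearson chi-square gives 87.7%. The comparisons below use that exact basis. The interim look is not included.

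**Step 2: tests compared.** In stratum i, let n_Ai and n_Bi be the arm sizes, n_i their sum, x_Ai the responders in Arm A and m_i all responders.

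- CMH without continuity correction: [Σ(x_Ai − n_Ai·m_i/n_i)]² / Σ[n_Ai·n_Bi·m_i(n_i − m_i)/(n_i²(n_i − 1))].
- The comparator is the pooled, uncorrected chi-square.
- Stratum rates are solved so that each arm's mean stays at 0.20 or 0.60. At OR 4 with equal strata they are 0.10 and 0.30 in the lower arm, and 0.44 and 0.76 in the higher arm.
- All outcomes in 2 strata × 2 arms are enumerated.

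**Step 3: power with equal strata, chi-square vs CMH.** In the dropout column, 2 of 24 per arm are lost at random from 12 + 12, independently in each arm.

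| OR | Exactly balanced (11 + 11) | Averaged over dropout |
|---|---|---|
| 1 | 87.7% vs 87.2% | 87.7% vs 87.3% |
| 2 | 87.9% vs 87.9% | 87.9% vs 88.1% |
| 3 | 88.3% vs 89.0% | 88.2% vs 89.2% |
| 4 | 88.6% vs 90.1% | 88.5% vs 90.2% |
| 8 | 89.7% vs 92.9% | 89.5% vs 92.8% |

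**Step 4: unequal strata, exactly balanced between arms.** Changes are in points of power, computed before rounding. With 7 to 15 of 22 per arm in the higher-response stratum:

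- OR 1: -0.6 to -0.5
- OR 2: -0.3 to 0.0
- OR 3: +0.2 to +0.7
- OR 4: +0.7 to +1.4
- OR 8: +2.2 to +3.3

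With a very small stratum the gain largely goes. With 3 of 22 in the higher-response stratum it is +0.2 at OR 4 and +1.2 at OR 8. With 3 of 22 in the lower-response stratum it is -0.3 and -0.2.

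**Step 5: imbalance among evaluable patients.** With 12 of 24 in each stratum and 2 lost at random, an arm keeps 10, 11 or 12 higher-response patients with probabilities 0.239, 0.522 and 0.239.

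- Same mix in both arms: 0.522² + 2×0.239² = 38.7%.
- Differ by one patient: 2×0.522×0.478 = 49.9%.
- Differ by two patients: 2×0.239² = 11.4%.

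Power at a two-patient difference (12/10 vs 10/12), chi-square vs CMH:

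| OR | Better arm has fewer higher-response patients | Better arm has more |
|---|---|---|
| 2 | 85.9% vs 88.3% | 89.7% vs 89.1% |
| 4 | 84.6% vs 90.2% | 91.9% vs 91.3% |

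**Step 6: type I error, balanced strata.** At null rates of 0.2, 0.3 and 0.4 the chi-square has size 0.107, 0.109 and 0.098 at OR 1. The excess over 0.10 comes from discreteness. At OR 8 its size is 0.077-0.102, 0.073-0.102 and 0.061-0.087, depending on the stratum share. CMH stays at 0.084-0.105 over OR 1 to 16 and null rates 0.2 to 0.6.

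**The case against.** The strongest reply is that nothing is wrong: an unadjusted test after stratified randomisation is valid, and the gain depends on an odds ratio that the documents do not supply. Much of the background in Section 2.1.2 points towards a weak effect. It says "CLL patients typically respond poorly to vaccines, particularly pneumococcal polysaccharide and influenza vaccines". In one cited series "no patients in this series had a response to the polysaccharide pneumococcal vaccine". In another study, which also found poor responses overall, "a significant correlation was demonstrated with less advanced disease stage and absence of hypogammaglobulinemia", so the predictors named there are not prior vaccination. A higher baseline also makes a four-fold rise harder, and Section 13.2 describes the measures as changes from baseline. All of this stands, and it is why the point is modest.

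The two-patient imbalance is also a tail case. It has probability 11.4% under the dropout model, and only half of that, 5.7%, disadvantages the better arm. Averaged over dropout at OR 4 the CMH gain is 1.6 points, against 1.4 with exact balance, so dropout adds little on average. What CMH offers here is less dependence on chance mix: power moves by 1.1 points (90.2% to 91.3%) rather than 7.3 (84.6% to 91.9%).

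A change of primary test would also have to cover the interim look at 11 per arm (p < 0.0056). CMH can carry that look, at a cost of about 0.5 points of power there at OR 1 and with a gain from OR 3.

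Finally, Section 9 says the study's endpoints have been reached, so a change of primary test may come too late. The fix allows for that.

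**Conclusion.** The concern holds as a recommended improvement, not as an error. The primary analysis ignores the only factor used to stratify randomisation, and the plan gives no reason. If prior vaccination has an odds ratio of 1 to 2 for response, a stratified test gains essentially nothing and may lose up to about half a point of power. At OR 4 it gains roughly 1 to 1.5 points and at OR 8 roughly 2 to 3, unless one stratum is very small. It also keeps power nearly constant when the evaluable arms differ in stratum mix.

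These figures assume two strata and a common odds ratio in both arms, and the dropout figures also assume losses at random. Neither the stratum share nor the odds ratio can be checked from the documents.

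**What to change.** In Section 13.3, name as the primary comparison, at both the interim and the final analysis, a CMH test without continuity correction, stratified by pneumococcal vaccination in the previous 5 years. Report a Mantel-Haenszel risk difference with its confidence interval. Keep the unstratified chi-square as a sensitivity analysis.

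If the primary analysis has already been done, do not change the primary test, because that would be post hoc. Leave the chi-square as primary, report the CMH result as a labelled sensitivity analysis, and tabulate stratum counts by arm among evaluable patients.

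The cost is some wording and a few lines of code, since the stratum is already recorded at randomisation. If the stratum does not predict response, the price is 0.5 to 0.6 points of power with exactly balanced strata of moderate size (7 to 15 of 22), and about 0.2 to 0.4 points under the dropout in Section 13.4.
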